12.4.2 Statistical model, hypothesis, and method of analysis

For all primary endpoints, summaries at baseline, Month 3, 6, 9 and 12 post-indexing date will be reported together. Different hypothesis testing will be done on different types of variables as follow:

Analysis of paired patient proportions

Occurrence events to be considered SVT, NSVT, PVC, ICD shocks and ATP.

For each of the occurrence event, number of patients with at least one event stratified by treatments, will be presented in a 2 x 2 contingency table as follow:

Table 12-1 Matched pairs 2 x 2 contingency table

ARNI (case)	ACEI/ARB (control)		
	At least one event	No event	Total
At least one event	а	b	a + b
No event	С	d	c + d
Total	a + c	b+d	N = a + b + c + d

The following statistical hypothesis under 95% significance level will be tested to address the primary objective:

Null hypothesis: $p_b = p_c$ versus alternative hypothesis: $p_b \neq p_c$, where p_b and p_c is b/N and c/N respectively. The test statistic considered is McNemar Test statistic as follow:

$$\chi^2 = \frac{(b-c)^2}{b+c}$$

which has a chi-squared distribution with degree of freedom of one.

However, an exact test (binomial sign test) will be used if the discordant cells have low values (b + c < 25).

12.4.3 Handling of remaining intercurrent events of primary estimand

The analysis will account for different intercurrent events as explained in Section 2.1.

12.4.4 Handling of missing values not related to intercurrent event

No assumptions on the type of missing data will be made (missing completely at random etc.). The comparison using McNemar Test required the proportion observed to be in pair, hence the analysis will be done on complete-case basis.

12.4.5 Sensitivity analyses for primary endpoint/estimand

None.

12.4.6 Supplementary analysis

None.

12.4.7 Supportive analyses

In addition to the primary analysis, all the paired proportion will also be analyzed using the Liddell's exact test (Liddell 1983) as supportive analysis. From Table 12-1, the maximum likelihood estimate of relative risk (Mantel and Haenszel 1959), \hat{R} is given as follow:

$$\hat{R} = \frac{b}{c}$$
.

Null hypothesis: $\hat{R} = 1$ versus alternative hypothesis: $\hat{R} \neq 1$. The test statistic considered, F is given as follow:

$$F = \frac{b}{c+1}$$

which has a F-distribution with degrees of freedom of 2(c+1) and 2b. Two-sided probability and 95% confidence interval of estimated relative risk will be presented as well.

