12.8 Sample size calculation

12.8.1 Primary endpoint

McNemar Test is used in the primary analysis to test for 2 correlated proportions. Approximate formula from Machin et al (1997) is used to calculate the minimum size required.

For the proportion of discordant pairs, the following approximate formula is used:

Proportion Discordant =
$$P_t(1 - P_s) + P_s(1 - P_t)$$

where P_t and P_s are proportion of patients experiencing the event of interest during ACEI/ARB and ARNI treatment period respectively. Over here, both proportions are assumed to be similar to de Diego et al (2018)'s study. According to de Diego et al (2018)'s study, SVT (one of the VA event) has the following incidence 8/120 and 1/120 during ACEI/ARB and ARNI treatment period respectively. Hence, by substitute both into the equation above, proportion discordant calculated is 0.0739 after rounding off.

For the difference, a parameter under effect size is approximated by the following formula:

Effect Size =
$$P_t(1 - P_s) - P_s(1 - P_t)$$

and after substituting P_t and P_s defined above, the effect size calculated is -0.0583.

Thus, by considering the parameters defined above, power of 0.8 and significance level of 0.05, the sample size required is 175. Further consider a dropout rate of 20%, the minimum sample size required is 219.

The above calculation is calculated using PASS 11 software's Test for Two Correlated Proportion (McNemar Test) [Differences] procedure.

For proportion of patients had ICD or CRT-D shocks occurrence over 6 months of ACEI/ARB and 6 months of ARNI treatment, the above sample size will provide 95% - 98% power to detect a proportion difference of 0.075 at two-sided significance level of 0.05. The proportion difference is derived from the published literature (de Diego et al 2018).

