3.4 Interim analyses

The interim analysis (IA) and endpoint analysis will be performed in this study. An interim analysis will be performed when half of the required sample size (110 patients) have completed the 12-month treatment and follow-up period or prematurely withdrawn from study after at least one ARNI treatment, aiming at analyzing the study endpoints and safety, as well as re-evaluating the minimum sample size required.

For this interim analysis, the efficacy analysis will include efficacy data from 117 eligible subjects (i.e., subjects who have used ARNI at least once before freezing of the interim analysis data and completed the trial or early withdrawn).

Other analyses include all data from these 117 subjects and all subjects enrolled before these subjects.

4. Study Endpoints

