7.1 Overall Statistical Considerations

All statistical analyses are performed using SAS9.4.

All subjects related, efficacy related and safety related data should be collected and included in the statistical analysis. Notes or descriptive text records are only listed. For other data, descriptive statistical analysis would be performed, also statistical inference would be applied if needed.

In the statistical tabulations, screening number of subjects is the universal unique identifier of subjects in the study.

General rules of descriptive statistics: Quantitative variables are described by mean, standard deviation, standard error, median, minimum, maximum, Q1 and Q3. Categorical variables are

described by number and percentage of each category. Two-sided 95% confidence intervals will also be calculated for efficacy endpoints.

In the laboratory test part and the efficacy analysis part, 2 digits will be retained for the upper and lower limits of means and their confidence intervals, 3 digits for standard deviations, and 2 digits for medians, minimums, maximums, Q1 and Q3. In other parts, 1 digit more than the original values can be retained for the upper and lower limits of means and their confidence intervals, 2 digits more for standard deviations, and the original value digits for medians, minimums, maximums, Q1 and Q3. One decimal place will be retained for percentages and the upper and lower limits of their confidence intervals (but for efficacy analysis, 2 decimal places will be retained).

General principles of statistical inference: paired t test and Wilcoxon rank sum test will be used to compare quantitative data. McNemar test, exact test (binomial sign test) and Liddell's exact test will be used to compare categorical variables. All statistical tests will be subjected to twosided tests (unless otherwise specified), and a P-value less than or equal to 0.05 will be considered to indicate a statistically significant difference (unless otherwise specified).

For values such as "< xxx", half of the number following the less-than sign will be used to summarize and calculate statistics. For values such as "> xxx", xxx will be used to summarize and calculate statistics. For values such as "xx-xx", the average of the numbers before and after "-" will be used to summarize and calculate statistics. P value is rounded to 4 decimal places. If P < 0.0001, it is presented as '< .0001'; if P > 0.9999, it is presented as '> .9999'.

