7.4 Efficacy Analysis

7.4.1 Efficacy analysis of primary endpoint

The analysis will be based on the efficacy analysis set and the per protocol set.

- Proportion of paired patients who developed at least one SVT over 6 months of ACEI/ARB and 6 months of ARNI treatment.
- Paired proportion of patients by the occurrence of at least one NSVT over 6 months of ACEI/ARB and 6 months of ARNI treatment.
- Paired proportion of patients by the occurrence of at least one PVC over 6 months of ACEI/ARB and 6 months of ARNI treatment.
- Paired proportion of patients by the occurrence of at least one ICD or CRT-D shock over 6 months of ACEI/ARB and 6 months of ARNI treatment.
- Paired proportion of patients by the occurrence of at least one ATP event over 6 months of ACEI/ARB and 6 months of ARNI treatment.

Different hypothesis testing will be done on different types of variables:

Analysis of paired patient proportion

Occurrence events to be considered are SVT, NSVT, PVC, ICD or CRT-D shocks and ATP.

For each of the occurrence event, number of patients with at least one event stratified by treatments, will be presented in a 2×2 contingency table as follow:

ARNI (case)	ACEI/ARB (control)		
	At least one event	No event	Total
At least one event	a	b	a + b
No event	С	d	c + d
Total	a + c	b + d	N = a + b + c + d

Table 5-1 Matched pairs 2 × 2 contingency table

The following statistical hypothesis under 95% significance level will be tested to address the primary objective:

Null hypothesis: $p_b = p_c$ versus alternative hypothesis: $p_b \neq p_c$, where p_b and p_c are b/N and c/N, respectively. The test statistic considered is McNemar Test statistic as follow:

$$\chi^2 = \frac{\left(b-c\right)^2}{b+c}$$

which has a chi-squared distribution with degree of freedom of one.

However, an exact test (binomial sign test) will be used if the discordant cells have low values (b + c < 25).

Supportive analyses

In addition to the primary analysis, all the paired proportion will also be analyzed using the Liddell's exact test (Liddell 1983) as supportive analysis. From Table 5-1, the maximum likelihood estimate of relative risk (Mantel and Haenszel 1959), \hat{R} is given as follow:

$$\widehat{R} = \frac{b}{c}$$

Null hypothesis: $\hat{R} = 1$ versus alternative hypothesis: $\hat{R} \neq 1$ The test statistic considered, *F* is given as follow:

$$F = \frac{b}{c+1}$$

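### The supportive Liddell test is printed in a form that gives the exact p-value only when b > c, the opposite of the direction the trial expects, and its estimate b/c is a conditional odds ratio, not a relative risk

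*Protocol*

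**What the plan says.** Table 12-1 of the protocol (Table 5-1 in SAP 7.4.1) has ARNI in the rows and ACEI/ARB in the columns. So b counts patients with an event on ARNI only, c counts patients with an event on ACEI/ARB only, and a counts patients with events in both periods.

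The primary test is McNemar's chi-square, replaced by the exact binomial sign test when b + c < 25.

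The supportive analysis, Liddell's exact test, is applied to all five paired proportions:

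- **Estimate.** R = b/c, introduced in protocol 12.4.7 with "From Table 12-1, the maximum likelihood estimate of relative risk" and in SAP 7.4.1 with "From Table 5-1, the maximum likelihood estimate of relative risk".
- **Statistic.** F = b/(c+1), "which has a F-distribution with degrees of freedom of 2(c+1) and 2b". The SAP repeats it unchanged.
- **Output.** "Two-sided probability and 95% confidence interval of estimated relative risk will be presented as well".

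Neither document says that the larger discordant count goes in the numerator, which tail to use, how the interval is computed, or what to do when b or c is zero. SAP 7.1 lists Liddell's test among its inferential methods and sets one threshold for all tests: "a P-value less than or equal to 0.05 will be considered to indicate a statistically significant difference".

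**The concern.** The F form of this exact test depends on which discordant count is called b. The table fixes b by treatment, not by size, and if ARNI works b will be the smaller count. A programmer who follows the text in that case gets either an impossible p-value or one that is too small. Under the general threshold in SAP 7.1, a too-small supportive p could be called significant beside a primary exact p that is not.

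The label is a separate matter. Among matched pairs, b/c estimates the conditional odds ratio. The ratio of the two period proportions, which is what the primary objective concerns, is (a+b)/(a+c). The interval for b/c is also the only one specified for a between-period effect measure. Readers can work out (a+b)/(a+c) from the 2×2 table, but without an interval, and may take b/c for a risk ratio.

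**Working it through.** **Inputs.** Protocol 12.8.1: "SVT (one of the VA event) has the following incidence 8/120 and 1/120 during ACEI/ARB and ARNI treatment period respectively"; discordant proportion 0.0739, difference 0.0583 in size, power 0.8, N = 175, 219 after dropout. SAP 3.4: "the efficacy analysis will include efficacy data from 117 eligible subjects".

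**The plan's own figure.** Under the plan's independence formula:

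- p_b = (1/120)(112/120) = 0.00778
- p_c = (8/120)(119/120) = 0.06611
- Sum 0.0739, difference 0.0583

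The two-sided exact McNemar test has power 0.7994 at N = 174 and 0.8024 at N = 175, so 175 is reproduced, and 175/0.80 = 218.75, rounded up to 219. Expected counts at N = 175 are b = 1.4 and c = 11.6.

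**What the printed F computes.** Let X ~ Binomial(b+c, ½). For F = b/(c+1) on 2(c+1) and 2b degrees of freedom, the upper tail is P(X ≥ b) and the lower tail is P(X ≤ b−1). When b < c the exact two-sided p is 2P(X ≤ b), and neither doubled tail equals it.

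Example with b = 3, c = 10 (13 discordant pairs, 2^13 = 8192):

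- Exact: 2(1+13+78+286)/8192 = 2(378)/8192 = 0.092
- Doubled upper tail: 2(8192−92)/8192 = 1.98
- Doubled smaller tail: 2(1+13+78)/8192 = 2(92)/8192 = 0.022

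| b, c | Exact p | 2 × upper tail | 2 × smaller tail |
|---|---|---|---|
| 10, 3 | 0.0923 | 0.0923 | same |
| 3, 10 | 0.0923 | 1.978 | 0.0225 |
| 2, 9 | 0.0654 | 1.988 | 0.0117 |
| 1, 7 | 0.0703 | 1.992 | 0.0078 |
| 6, 15 | 0.0784 | 1.973 | 0.0266 |

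Over all tables with b from 1 to 60 and c from 0 to 60, the doubled upper tail matches the exact p in 1830 of 1830 tables with b > c. With b < c and the value capped at 1, it matches in only 59 of 1770, the cases c = b+1, where the exact p is 1.

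**How often it matters for sustained VT.** Enumerating (b, c) at the planning rates:

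| | N = 175 | N = 117 |
|---|---|---|
| b = 0, printed F undefined | 25.5% | 40.1% |
| b ≥ 1, b < c, smaller-tail p ≤ 0.05, exact p > 0.05 | 13.4% | 22.4% |

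At N = 175, b < c in 99.9% of trials and b > c in 0.04%. P(b + c ≥ 25) is 0.001, so the primary test is almost always the exact sign test, which a correct Liddell p equals. The N = 117 column assumes that every interim subject gives a complete pair.

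**Error rate under the null, smaller-tail reading, b = 0 left out as undefined.** With 13 discordant pairs, the total is 0.057 (0.046 favouring ARNI) against a correct 0.022 (0.011). With 9 pairs it is 0.107 (0.088) against 0.039 (0.020).

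**Zero cells.** At b = 0 the second degrees of freedom, 2b, are zero. The data still carry an answer: for b = 0, c = 12 the sign test gives p = 0.0005, the estimate is 0, and its exact upper limit is 0.36. At c = 0 the ratio b/c itself is undefined.

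**The label.** For sustained VT at the planning rates, b/c = 0.00778/0.06611 = 0.118, and the relative risk is (1/120)/(8/120) = 0.125, a negligible gap. The documents give no incidence for NSVT or PVC. As an assumption, take 40% on ACEI/ARB and 30% on ARNI, so the relative risk is 0.75, and vary the share a of patients with events in both periods:

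- a = 12% (independent periods): b/c = 18/28 = 0.64
- a = 20%: b/c = 10/20 = 0.50
- a = 25%: b/c = 5/15 = 0.33

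**Check of the remedy.** With r = max(b,c), s = min(b,c), F = r/(s+1) on 2(s+1) and 2r degrees of freedom, and p = min(1, 2 × upper tail), the exact p is reproduced in all 3660 of the tables above. It also works at b = 0: (0, 12) gives F = 12 on 2 and 24 degrees of freedom, p = 0.0005.

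**The case against.** The strongest reply concerns consequence, not arithmetic. The analysis is supportive and no decision is tied to it. Both documents name an exact test, and a programmer using a validated routine, or swapping the cells, would get the right p. A value near 2 would be caught in validation. Only the smaller-tail reading gives a plausible wrong answer, the text does not call for it, and the 13.4%, 22.4% and null-error figures all depend on it. A wrong supportive p would also sit beside the primary exact p that it should equal. The exact power at N = 175 is 80%, so at the planning effect the primary result would usually be significant anyway.

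Two narrower points also have force. An exact interval for b/c is valid in either direction (for b = 1, c = 8: 0.0028 to 0.932), so the formula error touches the p-value and not the interval. And b/c is written out, so what is computed is not in doubt; the larger label gaps use assumed rates.

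These points limit the size of the problem but do not remove it. The written rule gives no valid p in the direction the planning rates imply, and it cannot be computed at b = 0, which no choice of tail repairs. SAP 7.1 also promises confidence intervals for efficacy endpoints in general, but it names no other between-period effect measure, so b/c remains the only one with a specified interval.

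**Conclusion.** The point holds, and is confined to the supportive analysis. The McNemar and sign tests are symmetric in b and c and are sound.

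As printed, the F rule gives the exact p for b > c but not, apart from the trivial c = b+1 case, for b < c, and it has no value at b = 0. At the sustained VT planning rates with 175 independent-period pairs, that covers nearly every trial: b = 0 in 25.5%, and a false supportive significance in 13.4% if the smaller tail is doubled. These figures are for sustained VT only; the documents do not quantify the expected direction for NSVT or PVC.

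The relative-risk label is wrong in principle. It is harmless for sustained VT, and could mislead for endpoints where many patients have events in both periods, by an amount the documents do not allow one to fix. The correction should be made before the analysis is programmed, although it does not bear on the primary conclusion.

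**What to change.** In protocol 12.4.7 and SAP 7.4.1:

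1. Define r as the larger and s as the smaller of b and c. Use F = r/(s+1) on 2(s+1) and 2r degrees of freedom, and report twice the upper tail, capped at 1. If the interval is computed from r/s, invert the estimate and limits when b < c.
2. State the zero-cell rules: b = 0, estimate 0 with an exact upper limit; c = 0, exact lower limit only; both zero, no test.
3. Call b/c the conditional (matched-pair) odds ratio.
4. Report (a+b)/(a+c), the paired difference (b−c)/N, or both, with a 95% confidence interval, as the effect measure. This is a small addition beyond repairing the formula, but it answers the primary objective on its own scale.

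The cost is a few lines of text and little SAS code, with no new data. The only drawback is that reported reductions may look smaller than b/c would suggest.

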12.5 Analysis of secondary endpoints

12.5.1 Efficacy endpoints

Please refer to Section 2 for the secondary objectives. The corresponding secondary variables are listed below:

- 1. Paired numbers of VA (SVT and NSVT in separate), PVC, ICD and ATP over 6 months of ACEI/ARB treatment and 6 months of ARNI treatment
- 2. Change in LVEF from date of treatment initiation over 6 months of ACEI/ARB treatment and 6 months of ARNI treatment
- 3. Change of NYHA level over 6 months of ACEI/ARB treatment and 6 months of ARNI treatment
- 4. Change proportion of NT-proBNP from date of treatment initiation over 6 months of ACEI/ARB treatment and 6 months of ARNI treatment
- 5. Number of hospitalizations for all causes and HF related hospitalizations during ACEI/ARB and ARNI treatments

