8.3.2 Secondary efficacy endpoints

Number of occurrences of VA

The episodes of VA events over 6 months of ACEI/ARB and 6 months of ARNI treatment will be measured.

Left ventricular ejection fraction

Left ventricular ejection fraction (%) will be compared at baseline, Month 6 and EOS.

NYHA level

NYHA level will be recorded by investigators and compared at baseline, Month 6 and EOS.

NT-proBNP

The measurements of NT-proBNP will be obtained from serum and plasma. Samples will be obtained before patients take their morning study drug dose. NT-proBNP (pg/mL) will be compared between ACEI/ARB and ARNI treatments at baseline, Month 6 and EOS.

Number of hospitalizations

Number of hospitalizations for arrhythmia or HF related hospitalizations will be recorded during ACEI/ARB and ARNI treatments.

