12.5.2 Statistical model, hypothesis, and method of analysis

All the following analysis will be performed on the FAS and PP.

Analysis of change from date of treatment initiation after 6 months of treatment for paired quantitative endpoints

Variables involved are number of SVT experienced, number of NSVT experienced, number of hourly PVC experienced, number of ICD shocks experienced, number of ATP experienced and time duration of NSVT experienced.

For each variable, a summary table will be reported to show the changes from baseline to Month 3, and 6 post-indexing and changes from Month 6 to Month 9, and 12 post-indexing date. The changes will be summarized by mean, standard error, median, quartiles, minimum and maximum.

Amended Protocol Version 02 (Track changes)

The change from date of treatment in interested endpoint after 6 months of each treatment is calculated by taking the difference between value recorded at the date of first treatment intake and at the date of last treatment intake.

Normality will be checked for the changes calculated, if the data is parametric, paired t-tests will be performed; else if the data is non-parametric, Wilcoxon signed-rank test will be used.

Analysis of change from date of treatment initiation after 6 months of treatment for continuous endpoints

Variables involved are LVEF, NYHA and NT-proBNP.

For each variable, a summary table will be reported to show the changes from baseline to Month 3, and 6 post-indexing and changes from Month 6 to Month 9, and 12 post-indexing date. The changes will be summarized by mean, standard error, median, quartiles, minimum and maximum.

The change from date of treatment in interested endpoint after 6 months of each treatment is calculated by taking the difference between value recorded at the date of first treatment intake and at the date of last treatment intake.

Normality will be checked for the changes calculated, if the data is parametric, paired t-tests will be performed; else if the data is non-parametric, Wilcoxon signed-rank test will be used.

Other than that, the variables involved before and after the initiation of ARNI will also be analyzed using the same statistical method.

Note that NYHA is a qualitative variable, appropriate data transformation (to be described in Statistical Analysis Plan) will be used to convert it into quantitative form.

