Baseline definition: Visit 1 data will be used as baseline of ACEI/ARB, and Visit 4 data as baseline of ARNI. If Visit 4 data are missing, the last available data before Visit 4 will be used.

Unless otherwise specified, the statistical description by visit only included the data of scheduled visits. For the evaluation involving maximum change, minimum change, abnormality, and clinically significant findings, the data of scheduled visits and unscheduled visits should be included.

Adverse events and medical history will be coded using MedDRA (see DMP for the specific version number).

Prior medications and concomitant medications will be coded using WHO Drug Dictionary (see DMP for the specific version number).

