7.2.2 Derived and converted data

Except for the calculation of certain study endpoints based on the data collected from CRF, no other data are derived or converted. For outliers, data queries are reported to the DM and solved or verified before database lock. No special data processing is performed.

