7.4.2 Efficacy analysis of secondary endpoints

The analysis will be based on the efficacy analysis set and the per protocol set.

- Paired numbers of VA (SVT and NSVT in separate), PVC, ICD or CRT-D shocks and ATP over 6 months of ACEI/ARB treatment and 6 months of ARNI treatment.
- Change in LVEF from date of treatment initiation over 6 months of ACEI/ARB treatment and 6 months of ARNI treatment.
- Change of NYHA level over 6 months of ACEI/ARB treatment and 6 months of ARNI treatment.
- Change proportion of NT-proBNP from date of treatment initiation over 6 months of ACEI/ARB treatment and 6 months of ARNI treatment.
- Number of hospitalizations for all causes and HF related hospitalizations during ACEI/ARB and ARNI treatments.
- Paired numbers of VA (SVT and NSVT in separate), PVC, ICD or CRT-D shocks and ATP over 3 months of ACEI/ARB treatment and 3 months of ARNI treatment.
- Number of hospitalizations for all causes and HF related hospitalizations during 3 months of ACEI/ARB and ARNI treatments.

Analysis of change from date of treatment initiation after 6 months of treatment (for paired quantitative endpoints)

Variables involved are number of SVT experienced, number of NSVT experienced, number of hourly PVC experienced, number of ICD or CRT-D shocks experienced, number of ATP experienced and time duration of NSVT experienced, as well as number of hospitalizations for

all causes and HF related hospitalizations.

The number of occurrences or duration of each variable within 3 months and 6 months and their changes from baseline will be descriptively analyzed by treatment group and compared between groups. The changes will be summarized by mean, standard error, median, quartiles, minimum and maximum. Because the baseline and post-treatment device data collection cycles are different, data will be standardized on a daily basis before the analysis of changes.

Normality will be checked for the values of each variable and changes calculated. If the data is parametric, paired t-tests will be performed; else if the data is non-parametric, Wilcoxon signed-rank test will be used.

Analysis of change from date of treatment initiation after 6 months of treatment (for continuous endpoints)

[figure not shown]
Variables involved are LVEF, NYHA and NT-proBNP.

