The values of each variable at visits following 3 months and 6 months of treatment and their changes from baseline will be descriptively analyzed by treatment group and compared between groups. The changes will be summarized by mean, standard error, median, quartiles, minimum and maximum.

Normality will be checked for the values of each variable and changes calculated. If the data is parametric, paired t-tests will be performed; else if the data is non-parametric, Wilcoxon signed-rank test will be used.

NYHA is a qualitative variable, and NYHA level will be subject to Ridit transformation into a numerical Ridit value before the above analysis is carried out. The basic idea of Ridit transformation is to first determine a standard group (the sum of the frequencies of each treatment group of each grade is taken as the standard group), and then obtain the Ridit value R of each grade of the standard group. The weighted average of the frequency of each grade in each group and the R value of each grade in the standard group will be respectively used to obtain the average Ridit value of each group, and then compare between groups.

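### NT-proBNP is declared as a proportional change, the Protocol computes an absolute one and the SAP names no scale; with equal proportional falls in both periods, the absolute change-score comparison shifts against ARNI

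*Protocol*

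**What the plan says.** **Declared endpoint.** Protocol 12.5.1 lists a plain change for LVEF, but for NT-proBNP: "Change proportion of NT-proBNP from date of treatment initiation over 6 months of ACEI/ARB treatment and 6 months of ARNI treatment". SAP 7.4.2 carries over the same term: "Change proportion of NT-proBNP from date of treatment initiation".

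**Protocol method.** Section 12.5.2 puts three variables under one rule: "Variables involved are LVEF, NYHA and NT-proBNP". For all three, the change is "calculated by taking the difference between value recorded at the date of first treatment intake and at the date of last treatment intake". There is no division by baseline and no logarithm. Protocol 8.3.2 gives the unit: "NT-proBNP (pg/mL) will be compared between ACEI/ARB and ARNI treatments at baseline, Month 6 and EOS".

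**SAP method.** SAP 7.4.2 drops the Protocol's formula and says: "The values of each variable at visits following 3 months and 6 months of treatment and their changes from baseline will be descriptively analyzed". It specifies Ridit scoring for NYHA but no ratio, percentage or log for NT-proBNP. SAP 7.2.2 adds: "Except for the calculation of certain study endpoints based on the data collected from CRF, no other data are derived or converted". The excepted endpoints are not named.

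**Baselines.** SAP 7.1: "Visit 1 data will be used as baseline of ACEI/ARB, and Visit 4 data as baseline of ARNI".

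**Tests.** Both documents choose between a paired t-test and the Wilcoxon signed-rank test after a normality check. Both also plan to compare the values themselves: Protocol 12.5.2 before and after the start of ARNI, and SAP 7.4.2 the values alongside the changes.

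**The concern.** Comparing the NT-proBNP change between treatments is a stated secondary objective (Protocol Table 2-1, SAP 2.2). The endpoint list and the Protocol's method use different scales, and the SAP does not settle which applies. Two programmers could follow the documents faithfully and produce different analyses, in an open-label trial where results can be seen as they accrue.

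The scale matters because the periods follow one another. Any fall during ACEI/ARB lowers the starting point for ARNI, and the same percentage fall from a lower start is a smaller fall in pg/mL. The absolute comparison can then report a treatment difference that the declared endpoint does not contain, or hide one that it does.

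**Working it through.** **What the plan quantifies.** The only NT-proBNP figure is in Protocol 12.8.2 (SAP 3.2.2): 84–91% power for a difference of 3 with SD 15, two-sided 0.05, shared with LVEF and without units. For a paired comparison, power = Φ(√n × 3/15 − 1.96):

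- n = 219: Φ(2.960 − 1.96) = 84.1%
- n = 175: Φ(2.646 − 1.96) = 75.4%
- n = 275 (the superseded sample size): Φ(3.317 − 1.96) = 91.3%

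Only the lower end is reproduced at the current sample size. That is a separate matter. Here the relevant fact is that the statement gives no NT-proBNP level and no expected fall, so B and r below are assumptions.

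**Algebra.** Let the Visit 1 value be B, with the same proportional fall r in each period.

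- Visit 4 = B(1 − r); Visit 7 = B(1 − r)²
- ACEI/ARB absolute change = −rB
- ARNI absolute change = −r(1 − r)B
- ARNI minus ACEI/ARB = r²B
- Proportional changes: −r and −r, difference 0

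Example with B = 2000 and r = 20%: 2000 → 1600 → 1280. The absolute changes are −400 and −320, so ARNI looks 80 pg/mL worse; both proportional changes are −20%.

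Values of r²B in pg/mL:

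| B | r = 10% | 20% | 30% | 40% |
|---|---|---|---|---|
| 1000 | 10 | 40 | 90 | 160 |
| 2000 | 20 | 80 | 180 | 320 |
| 4000 | 40 | 160 | 360 | 640 |

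**Effect on the planned tests.** Simulation with assumed inputs: lognormal values, median 2000 pg/mL at Visit 1, between-patient log-SD 0.9, n = 175, 1,000 runs per setting. Each cell gives the result for visit-level log-SD 0.3, then 0.5. The nominal rate in one direction is 2.5%.

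| Equal r | Absolute change, Wilcoxon: ARNI worse | Absolute change, paired t: ARNI worse | Log ratio: ARNI worse | Month 12 v Month 6 values, Wilcoxon: ARNI better |
|---|---|---|---|---|
| 0 | 7.4%, 12.0% | 2.7%, 3.6% | 3.5%, 2.5% | 2.8%, 3.0% |
| 10% | 9.6%, 15.4% | 4.7%, 5.1% | 2.3%, 3.3% | 81.4%, 40.2% |
| 20% | 20.2%, 21.9% | 8.8%, 6.1% | 3.2%, 2.2% | 100%, 95.2% |
| 30% | 64.3%, 44.9% | 33.8%, 15.8% | 2.2%, 2.3% | 100%, 99.9% |
| 40% | 98.8%, 80.5% | 84.1%, 42.6% | 3.4%, 2.4% | 100%, 100% |

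With a log-SD of 0.45 for the within-period change, the Wilcoxon rates at 20%, 30% and 40% are 23–26%, 58–63% and 97–98%. At r = 0 there is no r²B shift. The Wilcoxon excess there comes from the skewed distribution of Visit 1 + Visit 7 − 2 × Visit 4, so part of the rate at small r is not due to r²B.

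Check on the mean shift at visit-level log-SD 0.3: mean baseline = 2000 × exp(0.9²/2) × exp(0.3²/2) ≈ 3137. Multiplying by r² gives 125, 282 and 502 at 20%, 30% and 40%; the simulation gave 128, 279 and 504.

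**ARNI truly better (30% fall, then 40%).** 2000 → 1400 → 840. The absolute changes are −600 and −560, so ARNI still looks 40 pg/mL worse. In simulation the absolute Wilcoxon test was significant in about 11–14% of trials, nearly all against ARNI. The log ratio detected the benefit in 39–91%, depending on the noise.

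**Fall of 20%, then no further change.** The log ratio calls ARNI worse in 66–98% of runs, and the absolute Wilcoxon in 83–98%.

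**The case against.** Four objections carry weight.

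- **The size is assumed.** The documents give no NT-proBNP level, fall or spread, and do not say that the value will have fallen by Visit 4. Patients may enter already treated: Visit 1 records prior heart-failure drugs, and Protocol 6.2.1.1 asks for optimal background therapy. With r near zero the r²B shift vanishes. This stands.
- **The SAP does not prescribe absolute change.** It omits the Protocol's formula, and its exception for certain endpoints in 7.2.2 could cover a proportional change. This stands. The SAP's defect is an undefined scale; the contradiction lies between Protocol 12.5.1 and 12.5.2.
- **The Wilcoxon option deals with skewness.** It limits the pull of extreme values on a mean but does not remove the shift. In these simulations it is affected more than the t-test.
- **The other planned comparison points the other way.** Under equal falls, Month 12 versus Month 6 values favour ARNI. This stands.

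A reader might therefore infer that two equally effective drugs would necessarily show ARNI as worse, or that the NT-proBNP analysis as a whole is biased against ARNI. The documents support neither. The first holds only if equal efficacy means equal further proportional falls and the absolute scale is used; the second overlooks the comparison of values.

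**Conclusion.** The mismatch is certain: the declared endpoint is proportional, the Protocol's computation is absolute, and the SAP leaves the scale open. The consequence is conditional. Given equal proportional falls r from baseline B, the absolute change-score comparison shifts against ARNI by r² × B, and the declared scale shows nothing.

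Under the assumed median of 2000 pg/mL and n = 175, this is minor at r = 10% and severe at r = 30–40%. The paired t-test suffers less: 16–34% at r = 30%, against 45–64% for Wilcoxon across the noise range.

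The point is limited to the change-score comparison. It would also go too far to conclude that a log ratio makes the treatment comparison unbiased. It repairs the scale, but if NT-proBNP falls and then holds steady it also counts against ARNI, because the sequence is fixed and there is no concurrent control.

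**What to change.** 1. In Protocol 12.5.2 and SAP 7.4.2, take NT-proBNP out of the absolute-difference rule. Derive ln(Visit 4/Visit 1) for ACEI/ARB and ln(Visit 7/Visit 4) for ARNI, and compare them within patient with the plan's paired test.
2. Report the geometric mean ratio for each period, and their ratio, with 95% confidence intervals.
3. List the log ratio by name among the derived endpoints in SAP 7.2.2.
4. State that this is the main NT-proBNP comparison and that the comparisons of pg/mL values, including Month 12 versus Month 6, are supportive. At present the two can point in opposite directions with no stated priority.
5. State that the log ratio corrects the scale mismatch but does not remove confounding by period from the ACEI/ARB-then-ARNI sequence.

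Cost: one derived variable and a few lines of wording. Protocol Table 8-1 already schedules NT-proBNP at Visits 1, 4 and 7, so no new data are needed.
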